17.4. PK Analysis for Secondary Endpoints

The secondary endpoints of this study are the following, which are based on PK assessments (see [Table 2](#)) for BA (ETC-1002), EZE, and their metabolite (ESP15228, ETC-1002-glucuronide, and EZE-glucuronide) of milk and plasma PK samples.

- Amount excreted in breast milk during each collection period, calculated as the product of analyte concentration and volume of milk collected per collection period.
- Area under the breast milk concentration-time curve (AUC_{24h}) over the 24-hour collection interval. To calculate AUC_{24h} , the initial milk concentration at time equal 0 hours on Day 6 will be set equal to the value of C_{trough} for each individual subject.
- Average drug concentration in breast milk (C_{avg}) calculated as $AUC_{24h}/24h$
- Peak milk concentration (C_{max})
- Time of peak milk concentrations (T_{max})
- Trough milk concentrations at 24 hours after the last dose on Day 6 (C_{trough})
- Plasma trough concentrations at 24 hours after the last dose on Day 6 (C_{trough})

Actual sampling times will be used in the final analyses of individual PK parameters. Predose sampling times will be set to zero. AUC_{24h} will be estimated by noncompartmental analysis (linear up/log down trapezoidal method) and estimates of C_{max} and t_{max} will be reported from observed values. If C_{max} occurs at more than one time point, t_{max} will be assigned to the first occurrence of C_{max} .

C_{avg} in milk will be calculated based on area under the milk concentration-time curve (AUC_{24h}) over the 24-hour collection interval.

$$C_{avg} (\text{mg/mL}) = AUC_{24h} (\text{mg} \cdot \text{h/mL}) / 24h.$$

If a subject had fewer than 3 data points above LLOQ, AUC_{24h} and C_{avg} will be set to “NE” (Not Evaluable).

M/P ratio is defined as the ratio of milk trough concentration and plasma trough concentration.

$$\text{M/P ratio} = C_{trough} (\text{Milk}) / C_{trough} (\text{Plasma})$$

All the descriptive analyses on PK concentration and PK parameters will be performed upon the PKS.

Collected milk volume, milk concentration of BA and its metabolites will be summarized by nominal sampling timepoints, and by cohort on FAS. Milk concentration of EZE and its metabolite will be summarized by nominal sampling timepoints for Cohort 2 only.

Summary statistics of n, arithmetic mean, standard deviation (SD), CV%, minimum, median, maximum, geometric mean (converting back to the original units), and geometric coefficient of variation (GCV%) will be presented for PK concentration data and PK parameters (AUC_{24h} , C_{avg} , C_{max} , T_{max} , C_{trough}) by cohort in summary tables.

- Geometric mean = $\exp [\text{mean of log}(x)]$, exponential of mean of log-transformed concentration data.
- Geometric standard deviation (GSD) = $\exp [\text{SD of log}(x)]$, exponential of standard deviation of log-transformed concentration data.
- GCV% = $\sqrt{\exp (GSD^2) - 1} \times 100$.

The following assessments will also be summarized by cohort:

- Daily infant dosage ($Dose_{ij}$)
- Estimated daily infant dosage
- RID
- M/P ratio

Plots of the following milk concentration-time profiles will be created:

- (A) ETC-1002, (B) ESP15228, (C) ETC-1002-glucuronide on linear scale by cohort.
- (A) EZE, (B) EZE-glucuronide on linear scale for Cohort 2.
- Composite of individual subject (A) ETC-1002, (B) ESP15228, (C) ETC-1002-glucuronide, (D) EZE, (E) EZE-glucuronide on linear scale by cohort.

Box plot of the following parameters from breast milk PK will be created by cohort:

- C_{max} , C_{trough} , C_{avg} , and AUC_{24h} (A) ETC-1002, (B) ESP15228, (C) ETC-1002-glucuronide, (D) EZE, (E) EZE-glucuronide by cohort

All milk and plasma PK concentration data and parameters will be displayed in subject listings.

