#### **10.3.4.2 Treatment Day 6**

The 24-hour breast milk collection will start the morning of Day 6 and end the morning of Day 7. The following assessments/procedure will be performed prior to the initiation of the 24-hour breast milk collection:

- adverse event review;
- concomitant medication review; and
- subject will pump both breasts with an electric pump until empty prior to administration of the last dose of IMP.

Once both breasts have been completely emptied on the morning of Day 6, Cohort 1 subjects will receive the Day 6 dose of bempedoic acid and Cohort 2 subjects will receive the Day 6 dose of bempedoic acid/ezetimibe FCDP. Breast milk will be collected from each subject over the next 24 hours using an electric pump at 3, 6, 9, 12, 16, 20 and 24 hours ( $\pm 30$  minutes) after Day 6 dose administration.

At each collection time point, subjects will pump both breasts until empty, breast milk collected from each breast will be mixed together and the total volume measured and recorded. Breast milk from each time point will be stored according to procedures outlined in the Laboratory Manual and [Section 11.1](#).

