## **11. PHARMACOKINETIC ASSESSMENTS**

### **11.1 Breast Milk Sample Collection and Processing**

Breast milk will be collected using an electric pump. Breast milk samples will be collected within 1 hour before IMP dosing (predose) on Day 1 and on Day 6 at 3, 6, 9, 12, 16, 20 and 24 hours ( $\pm$ 30 minutes) after IMP dosing on Day 6. Subjects will be instructed to completely empty both breasts at each sampling time point. At each sampling time point, milk collected from each breast will be mixed together and the total volume will be measured and recorded. From each combined sample 2 aliquots (approximately 5 mL) of breast milk will be transferred to appropriately labeled tubes and stored at or below -70° Celsius within 30 minutes of collection. Breast milk samples from each time point will be stored according to procedures outlined in the Laboratory Manual.

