17. PHARMACOKINETIC (PK) ANALYSIS

17.1. PK Nominal Timepoints

Table 1 Schedule of Dosing and Sample Collection

Time	Day 1	Day 2	Day 3	Day 4	Day 5	Day 6	Day 7
Dosing (once per day)	X	X	X	X	X	X	
Sample	Plasma, Milk					Milk*	Plasma, Milk*

*On Days 6-7, breast milk will be collected during the intervals of 0-3h, 3-6h, 6-9h, 9-12h, 12-16h, 16-20h, and 20-24h after Day 6 dose administration

PK milk samples will be collected at the following nominal timepoints –

- Visit T1 (Day 1) Pre-dose (\leq 1 hour before IMP administration)
- Visit T2 (Day 6 and 7) at 3, 6, 9, 12, 16, 20 and 24 hours (\pm 30 minutes) after Day 6 dose administration.

PK plasma samples will be collected at the following nominal timepoints –

- Visit T1 (Day 1) Pre-dose (\leq 1 hour before IMP administration)
- Visit T2 (Day 7) at 24 hours (\pm 30 minutes) after Day 6 dose administration.

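### Each Day 6-7 milk sample is a 3-4 hour pool, but SAP 17.4 treats it as a spot value at the pumping time, so milk Tmax is reported late; the effect on AUC24h, Cavg and RID is negligible.

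*SAP*

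**What the plan says.** **How the milk is collected.** Protocol 10.3.4.2 requires on Day 6 that the "subject will pump both breasts with an electric pump until empty prior to administration of the last dose of IMP". Protocol 11.1 then states: "Subjects will be instructed to completely empty both breasts at each sampling time point". The milk from the two breasts is mixed and its total volume recorded. The note to SAP Table 1 (SAP 17.1) describes the result as interval collections: "breast milk will be collected during the intervals of 0-3h, 3-6h, 6-9h, 9-12h, 12-16h, 16-20h, and 20-24h".

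**How it is timed and analysed.** The same SAP section gives the milk samples nominal times "at 3, 6, 9, 12, 16, 20 and 24 hours" after the Day 6 dose, which are the ends of those intervals. SAP 17.4 adds: "Actual sampling times will be used in the final analyses of individual PK parameters". AUC24h "will be estimated by noncompartmental analysis (linear up/log down trapezoidal method"), and Cmax and Tmax are read from the observed values. The curve needs a value at time zero on Day 6. SAP 8.4.2 and 17.4 impute it from the 24 h milk concentration.

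**Where the results go.** Peak milk concentration, its time, milk trough and AUC24h are secondary endpoints (SAP 3.2). Cavg is AUC24h/24 h, and SAP 17.3 multiplies it by 150 mL/day/kg to obtain the RID numerator. The other primary endpoint, daily infant dosage, is the sum of concentration times volume over the collections and uses no time axis.

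**The concern.** A pool emptied at 6 h after a previous emptying at 3 h holds milk secreted between 3 and 6 h. Placing its concentration at 6 h moves it to the right by half an interval on average, and the whole milk profile moves with it. A reader who asks when drug secretion into milk is highest would get an answer displaced in one direction, with a precision that 3-4 h pools cannot give. The label Ctrough has the same weakness: the 24 h milk value is the 20-24 h average, yet the M/P ratio divides it by a plasma spot sample taken at 24 h. Because Cavg comes from the same trapezoid, the effect on RID also has to be sized.

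**Working it through.** **1. The plan's own figure.** Protocol 4.3 gives a half-life of about 24 h and says six daily doses reach about 98% of steady state. Check: 1 − 0.5^(6×24/24) = 1 − 0.5^6 = 98.4%. It reproduces.

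**2. Inputs.** From the documents: once-daily dosing for 6 days, half-life 24 h, and intervals 0-3, 3-6, 6-9, 9-12, 12-16, 16-20 and 20-24 h. Assumed, because the documents give no value: absorption rate ka of 0.2, 0.3, 0.5, 1 or 2 per h; lag of 0 or 2 h; half-lives of 12 and 6 h as sensitivity; milk concentration proportional to plasma; constant secretion; no re-equilibration before pumping.

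**3. Model.** With k = ln 2 / half-life, the Day 6 profile is the sum over the six doses of ka/(ka−k) × [exp(−k·s) − exp(−ka·s)], where s is time since that dose minus the lag, for s > 0. Pool i is the mean of this curve over interval i. Under the SAP rule, reported Tmax is the end of the interval with the highest pool.

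**4. Results at a 24 h half-life.**

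| ka (/h) | lag (h) | true peak (h) | highest pool | SAP Tmax (h) | delay (h) | AUC24h error |
|---|---|---|---|---|---|---|
| 0.2 | 0 | 7.40 | 6-9 h | 9 | 1.60 | +0.48% |
| 0.2 | 2 | 9.40 | 9-12 h | 12 | 2.60 | +0.43% |
| 0.3 | 0 | 6.14 | 6-9 h | 9 | 2.86 | +0.56% |
| 0.3 | 2 | 8.14 | 6-9 h | 9 | 0.86 | +0.54% |
| 0.5 | 0 | 4.61 | 3-6 h | 6 | 1.39 | +0.58% |
| 0.5 | 2 | 6.61 | 6-9 h | 9 | 2.39 | +0.60% |
| 1 | 0 | 2.95 | 3-6 h | 6 | 3.05 | +0.56% |
| 1 | 2 | 4.95 | 3-6 h | 6 | 1.05 | +0.60% |
| 2 | 0 | 1.81 | 3-6 h | 6 | 4.19 | +0.55% |
| 2 | 2 | 3.81 | 3-6 h | 6 | 2.19 | +0.58% |

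Tmax is late in every row. With half-lives of 12 and 6 h included (30 scenarios) it is still always late, by 0.2 to 4.2 h. The coarse grid alone does not explain this: at ka 1 per h with no lag, a true spot sample on the same schedule would put the peak at 3 h, not 6 h.

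**5. Why the AUC error is small.** With C0 = C24, the linear trapezoid minus the sum of C_i × interval length is 1.5 × (C0 − C12) + 2 × (C12 − C24) = 0.5 h × (C12 − C24). The time-zero imputation nearly cancels the shift. What remains comes from the change from 3 h to 4 h intervals while concentration falls.

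Example, ka 1 per h, no lag, pools relative to the last: 1.504, 1.642, 1.519, 1.394, 1.260, 1.122, 1.000.
- Sum of C_i × length = 3 × 6.059 + 4 × 3.382 = 31.705.
- Error = 0.5 × (1.394 − 1.000) = 0.197, and 0.197/31.705 = 0.62%. The log-down rule brings it to 0.56%.
- Varying pump times within ±30 min gives a mean of +0.55% (95% range +0.2% to +0.9%).

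At 12 h the error is +0.8% to +1.0%, and at 6 h +0.6% to +1.5%. RID carries the same percentage error. The sign is not universal: at assumed half-lives of 2 to 4 h with fast absorption it turns slightly negative (about −0.2% to −4%).

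**6. Cmax and Ctrough at 24 h.** The highest pool is 0.2% to 6.1% below the instantaneous peak. The 20-24 h pool is 5.4% to 6.0% above the concentration at 24 h.

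**The case against.** **The RID effect is trivial.** This stands. The analysis is descriptive, with 8 subjects per cohort and an assumed intake of 150 mL/day/kg. A reader might infer that a primary endpoint is materially inflated. The documents do not support that, because the error at their own half-life is about half a percent.

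**The two primary endpoints do not contradict each other.** Also right. Daily infant dosage uses the mother's expressed volume, and RID uses a standard intake per kg, so they would differ even with perfect timing.

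**Infant exposure follows removal of milk, not secretion.** Milk made between 3 and 6 h and expressed at 6 h would reach an infant at 6 h. The pumping time is a defensible label for that question, so it would be too strong to say the SAP misplaces peak infant exposure. No rule in either document uses Tmax. The delay concerns secretion timing only.

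**The remedy's accuracy is built into the model.** Pools were defined as interval means, so summing them over time must return the AUC. If milk re-equilibrates fully, so that a pool acts like a spot value, the sum misses the true AUC by −3.5% to +1.2% at a 24 h half-life, against −2.9% to +1.8% for the SAP rule. Neither is then clearly better, and the systematic Tmax delay disappears. The documents do not say which case applies.

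**Interval information is already visible.** Table 1 names the intervals, amounts per collection are summarised and all concentrations are listed. A careful reader could relabel Tmax, but the summary tables would still show a point time.

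**Conclusion.** The point holds as a low-cost correction of labels and method. SAP 17.1 defines interval samples, and SAP 17.4 analyses them as end-of-interval points. Under constant secretion and no re-equilibration, reported milk Tmax lies about 1 to 4 h after the true secretion peak at a 24 h half-life, and 0.2 to 4.2 h after it when 12 and 6 h are included. The size depends on the assumed absorption rates and lags. AUC24h, Cavg and RID are about 0.4% to 0.6% too high at 24 h, which is immaterial. Daily infant dosage is unaffected.

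**What to change.** In SAP 17.4 (and 8.4.2 for the imputation):

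- Report milk Tmax as the collection interval of the highest pool, for example 3-6 h. A midpoint is less suitable: it removes only 1.5 to 2 h and can fall early (7.5 h against a true 8.14 h).
- Label Cmax as the highest interval-average concentration and milk Ctrough as the 20-24 h pool, including where Ctrough enters the M/P ratio.
- Calculate AUC24h as the sum of C_i × actual interval length, and Cavg as that sum divided by total collection time. Drop the Day 6 time-zero imputation.
- Start the first interval at the pre-dose emptying. The documents record sample times relative to the dose but state no recorded time for that emptying, so record it or use the dosing time.

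The cost is a few sentences and a simpler calculation, with no new samples or assays. There are two small downsides. Tmax becomes an interval, which may still miss the peak (in 2 of the 10 rows above the true peak precedes the 3-6 h pool). AUC24h then assumes roughly constant milk secretion within each interval, which the SAP should state.

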## 14. STATISTICS

### 14.1 General Considerations

The statistical analysis described in this section will be performed as further outlined in a separate Statistical Analysis Plan (SAP). The SAP will supersede the protocol in the event of any difference between the 2 documents in data analysis and the protocol will be amended of appropriate. Statistical analyses in this study will be descriptive in nature. No statistical inference is planned. Subject disposition, demographics, and baseline characteristics will be summarized. Summary statistics for continuous variables will include the number of subjects, mean, median, standard deviation or standard error, first and third quartiles, minimum, and maximum. Summary statistics for PK parameters will also include geometric mean and coefficient of Variation (CV) (%). For categorical variables, the frequency and percentage will be given.

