1. INTRODUCTION

This statistical analysis plan (SAP) describes the rules and conventions to be used in the presentation and analysis of infant exposure, milk and plasma pharmacokinetic and safety data from healthy lactating women for Protocol 1002FDC-075, entitled *An Open-Label Postmarketing Milk-Only Lactation Study to Evaluate the Concentration of Bempedoic Acid and Bempedoic Acid and Ezetimibe in the Breast Milk of Healthy Lactating Women Administered Therapeutic Doses of Bempedoic Acid or Bempedoic Acid/Ezetimibe Fixed Combination Drug Product (FCDP)*, Amendment 1 (June 6th, 2023). The SAP will supersede the protocol in the event of any differences between the 2 documents in the plans for data analysis.

Analyses will be conducted using SAS® version 9.4 or higher and Phoenix WinNonlin version 8.4.

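### The SAP's geometric CV formula uses the exponentiated SD where the SD of log(x) belongs, so it can never return less than 131%, even with no variability

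*SAP*

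**What the plan says.** SAP section 17.4 closes with a list of summary statistics and their definitions. Three consecutive lines matter here:

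- The first back-transforms the average of the logs with exp to obtain the geometric mean.
- The second treats the spread in the same way: "Geometric standard deviation (GSD) = $\exp [\text{SD of log}(x)]$, exponential of standard deviation of log-transformed concentration data".
- The third builds the geometric CV from that result: "GCV% = $\sqrt{\exp (GSD^2) - 1} \times 100".

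The sentence above these lines says where the statistic appears: "geometric coefficient of variation (GCV%) will be presented for PK concentration data and PK parameters". Five milk parameters are listed there by name (AUC24h, Cavg, Cmax, Tmax and Ctrough), and each cohort is summarized separately.

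The protocol gives no competing formula. Section 14.1 names the statistic without defining it: "Summary statistics for PK parameters will also include geometric mean and coefficient of Variation (CV". SAP section 1 settles precedence: "The SAP will supersede the protocol in the event of any differences between the 2 documents in the plans for data analysis". The SAP line is therefore the governing specification.

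**The concern.** The geometric CV of log-normal data depends only on the SD on the log scale. The SAP exponentiates that SD once to form GSD, then puts GSD, not its logarithm, inside a second exponential. The result no longer measures variation, because it stays well above zero when all values are equal.

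The study is descriptive, with no inference planned (protocol section 14.1) and eight evaluable subjects per cohort. Measures of spread are therefore part of the reported result, and GCV% is the one that belongs beside each geometric mean. Cavg is one of the affected parameters, and SAP section 17.3 uses it to calculate the relative infant dose (RID). A CRO will perform the PK analyses (SAP section 5.2), so the written formula serves as the programming specification. If it is followed, the tables will overstate between-mother variability several-fold.

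**Working it through.** **Inputs.** Let s be the SD of log(x). From SAP section 17.4, GSD = exp(s). The log is natural, because the geometric mean in the same list is back-transformed with exp. The documents give no value of s, so values from 0 to 1.0 are assumed for illustration. They also state no GCV% figure, so there is nothing to reproduce first.

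**Formula as written.** GCV% = 100 x sqrt(exp(GSD^2) - 1), which in terms of s is 100 x sqrt(exp(exp(2s)) - 1).

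**Standard log-normal formula.** GCV% = 100 x sqrt(exp(s^2) - 1) = 100 x sqrt(exp([ln GSD]^2) - 1).

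**The floor.** An SD cannot be negative, so s >= 0 and GSD >= 1. The written formula increases with GSD, so its minimum is at GSD = 1: 100 x sqrt(e - 1) = 131.08%. This needs no assumption about s. It is also the correct geometric CV for s = 1.0, so the SAP would report complete absence of variability as if the log-scale SD were 1.

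**One case in full, s = 0.3.**
- As written: GSD = exp(0.3) = 1.3499; GSD^2 = 1.8221; exp(1.8221) = 6.185; sqrt(5.185) = 2.277, or 227.7%.
- Standard: s^2 = 0.09; exp(0.09) = 1.0942; sqrt(0.0942) = 0.307, or 30.7%.

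**Range.**

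| SD of log(x), assumed | GSD | GCV% as written | GCV% standard |
|---|---|---|---|
| 0 | 1.000 | 131.1 | 0 |
| 0.1 | 1.105 | 154.7 | 10.0 |
| 0.2 | 1.221 | 185.6 | 20.2 |
| 0.3 | 1.350 | 227.7 | 30.7 |
| 0.5 | 1.649 | 376.2 | 53.3 |
| 0.7 | 2.014 | 753.0 | 79.5 |
| 1.0 | 2.718 | 4021.4 | 131.1 |

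**Other readings tried.**
- Taking GSD to mean the log-scale SD gives the standard formula, but it contradicts the definition one line earlier, which is given in words as well as symbols ("exponential of standard deviation of log-transformed concentration data").
- Moving the -1 outside the square root, 100 x (sqrt(exp(GSD^2)) - 1), still gives 64.9% at s = 0.
- A symbol lost when the PDF was read is an unlikely explanation, because the verbal definition of GSD is intact and the GCV% line names GSD.

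**The case against.** The algebra is hard to dispute; the serious objection is to the consequence.

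- **The harm is conditional.** It arises only if the line is coded literally. A programmer using a standard built-in geometric CV would get the right numbers. This stands, but those tables would then depart from the SAP, so the text needs correcting in either case.
- **Spread is shown in other ways.** The same tables carry SD, arithmetic CV%, minimum, median and maximum, and the SAP also plans individual profiles, box plots and full listings. This stands. For log-normal data with s = 0.3, an arithmetic CV near 30% would sit beside a geometric CV near 228%. A careful reader might distrust the column instead of concluding that milk transfer is extremely variable. A column that has to be distrusted is still a defect.
- **The primary endpoints are not clearly touched.** Daily infant dosage, RID and the M/P ratio are to be summarized by cohort with no statistics named, and their formulas use neither GSD nor GCV%. This stands: no point estimate changes.
- **No decision depends on GCV%.** There is no test, no interim analysis and no variability-based sample size. This also stands.
- **Some summaries may have no GCV% at all.** Day 1 predose values below quantification are set to zero (SAP section 8.4.2), and log(0) is undefined. This is a small limit on scope and does nothing to rescue the formula.

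**Conclusion.** The formula is wrong as written. The SAP's own definitions of GSD and GCV% imply a minimum of 131.1%, with no outside figure needed. At illustrative log-scale SDs of 0.1 to 0.7, the stated formula gives 154.7% to 753.0% where 10.0% to 79.5% is correct. If implemented literally, it would make every computable geometric CV specified for concentrations and PK parameters wrong in both cohorts. The error is confined to that statistic; geometric means, arithmetic summaries and the point estimates for both primary endpoints stand.

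**What to change.** Replace the GCV% line in SAP section 17.4 with:

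GCV% = sqrt(exp([SD of log(x)]^2) - 1) x 100

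or, if GSD is to stay in the expression, sqrt(exp([ln GSD]^2) - 1) x 100. The GSD definition can remain unchanged.

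Check the table programs against the corrected line. A simple test is a set of identical positive values, which must return 0%. If output has already been produced from the stated formula, it need not be discarded: with the reported value as a proportion G, s = 0.5 x ln(ln(1 + G^2)). For example, G = 2.277 gives 1 + G^2 = 6.185, ln = 1.822 and s = 0.30, hence a correct GCV of 30.7%.

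The cost is one line of SAP text and a programming check. Data collection, subjects and timelines are unaffected.

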18. SAFETY ANALYSIS

18.1. General

All summary tables for safety outcomes will be based on the FAS. All adverse event tables will be summarized by cohort. There will be no statistical comparisons between cohort for safety data, unless otherwise specified.

